6.4.2 Analyses of Secondary Efficacy Endpoints

For dichotomous secondary efficacy parameters, similar analyses as the primary efficacy parameter will be used by time point, i.e., the Fisher's exact test for pairwise comparisons with placebo and the Cochran-Armitage test for trend.

For continuous efficacy parameters, the mixed model with fixed effects for treatment, time, treatment by time interaction, the stratification factors and the baseline, and measurements within each subject as repeated measures will be used.

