5.2.2 Secondary Efficacy Parameters

The secondary efficacy parameters (evaluated at Weeks 2, 4, 8, 12, 16 and EOT, respectively, unless otherwise stated):

- Percentage of subjects achieving ACR20/50/70 response rate (except ACR20 at EOT which is the primary parameter)
- Change from baseline in SDAI
- Percentage of subjects who achieved remission based on SDAI (≤ 3.3)
- Percentage of subjects who achieved low disease activity based on SDAI (≤ 11)
- Change from baseline in CDAI
- Percentage of subjects who achieved remission based on CDAI (≤ 2.8)
- Percentage of subjects who achieved low disease activity based on CDAI (≤ 10)
- Percentage of subjects achieving Boolean Remission
- Change from baseline in DAS28-CRP
- Percentage of subjects with DAS28-CRP of <2.6
- Percentage of subjects with DAS28-CRP of <3.2

- Percentage of subjects with good European League Against Rheumatism (EULAR) response at Week 12
- Percentage of subjects with moderate EULAR response at Week 12
- The lowest percentage change from baseline of 3 measures: tender joint count, swollen joint count and median change of the remaining 5 core measures (numeric ACR [ACR-N] index)
- Change from baseline in the Health Assessment Questionnaire Disability Index (HAQ-DI)
- Change from baseline in the number of tender and swollen joint counts (68/66 joints will be counted)
- Change from baseline in subject pain score by numeric rating scale (NRS)
- Change from baseline in subject global assessment (SGA) of disease activity by NRS
- Change from baseline in physician global assessment (PGA) of disease activity by NRS
- Change from baseline in hs-CRP

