6.1 Sample Size

Approximately 250 eligible subjects (50 in each treatment group) are randomized into the DB treatment period of this study.

The primary efficacy evaluation will be to compare the ACR20 response rate between JTE-051 with placebo at EOT. From one study comparing mavrilimumab with placebo in combination with stable MTX, the ACR20 of mavrilimumab and placebo at Week 12 were 0.69 and 0.40, respectively. Assuming the ACR20 of at least one of the JTE-051 doses to be at least 0.30 above placebo, the following sample size per group will be needed to detect a statistical significant difference at the 5% level with about 80% power (using 2-sided Fisher's exact test):

Placebo ACR20	0.25	0.35	0.45
Sample size per group	47	48	47

About 50 randomized subjects per group would therefore give at least an 80% power for a range of placebo responses. The sample size calculation was carried out using the software SiZ 6.2 (Cytel Inc., 2013).

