6.4.3 Supportive Analyses of Efficacy Parameters

For dichotomous efficacy parameter analysis with multiple time points, a supportive analysis will be performed using a generalized estimating equation (GEE) method on the logit scale. The model includes effects for treatment, time, treatment by time interaction, stratification factors and subject as the repeated factor. The odds ratio (OR) of each JTE-051 dose group relative to placebo at the same time point will be estimated.

Model: (generalized estimating equation (GEE) method on the logit scale)

```
proc genmod data=xxxx;
  class usubjid trtn(ref=1) region(ref=0) hscrpn(ref=0);
  model SAEP=trtn time trtn*time regionn hscrpn;
  repeated subject=usubjid/type=un corrw;
run;
```

[figure not shown]
Note: SAPE denotes any dichotomous efficacy parameter, regionn and hscrpn are stratification factors, we can add other stratification when needed.

The supportive efficacy parameters utilizing the non-hs-CRP will be analyzed in a similar manner as their secondary efficacy counterparts using hs-CRP.

All analyses will be performed two-sided at the 5% significance level. No formal multiple comparison adjustment will be made; therefore, results should be interpreted with the multiplicity in mind. The estimated treatment effect (relative to placebo), e.g., odds ratio, from the model, along with a two-sided 95% confidence interval (CI) and p-value, will be tabulated where appropriate. The Newcombe's CI of the rate difference between JTE-051 dose and placebo will be computed when performing the Fisher's exact test. Graphical presentations of the treatment profile will be depicted for the primary and key secondary analyses. Sensitivity analysis and model fit assessment may be conducted, and data transformation may be employed if appropriate.

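### Remission and low-disease-activity endpoints with fixed cut-offs are tested without the baseline of the same index; the cost is some precision, and its size depends on a correlation the documents do not give

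*SAP*

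**What the plan says.** SAP 5.2.2 defines six secondary endpoints by a fixed level of an index. Examples are "Percentage of subjects who achieved remission based on SDAI" (at most 3.3) and "Percentage of subjects who achieved low disease activity based on CDAI" (at most 10). The others are SDAI at most 11, CDAI at most 2.8, and DAS28-CRP below 2.6 and below 3.2. Boolean remission (SAP 5.2.5.6) is a seventh: four thresholds that must all be met. All are evaluated at five visits and at EOT.

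- **Main analysis, SAP 6.4.2.** Dichotomous endpoints are handled like the primary one, by time point: "i.e., the Fisher's exact test for pairwise comparisons with placebo and the Cochran-Armitage test for trend". Neither test takes a covariate.
- **Supportive analysis, SAP 6.4.3.** This is a GEE on the logit scale: "The model includes effects for treatment, time, treatment by time interaction, stratification factors and subject as the repeated factor". The printed code contains treatment, time, their interaction, region and hs-CRP category, and no baseline index.
- **Continuous forms of the same indices, SAP 6.4.2.** The mixed model includes the baseline. Protocol 3.8.3.2 gives Week 0 SDAI as its example.
- **Availability, SAP 5.1.** Baseline SDAI, CDAI and DAS28-CRP are derived for every subject.
- **Logistic models, SAP 6.4.1.** These carry baseline PGA, hs-CRP category and region, and are written for ACR20 at EOT.
- **Error rate, SAP 6.4.3.** "All analyses will be performed two-sided at the 5% significance level", with no multiplicity adjustment.

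**The concern.** ACR20 is measured relative to each subject's own start. A fixed cut-off is not. Entry criteria set a floor on joint counts and hs-CRP but no ceiling (Protocol 3.3.1), so starting levels can vary widely. As an illustration, reaching an SDAI of 11 needs a fall of (20 − 11)/20 = 45% from a start of 20, and (50 − 11)/50 = 78% from a start of 50.

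The baseline of the same index is therefore an obvious prognostic covariate, and the plan uses it for the continuous form and drops it for the dichotomised form. With 50 per arm, a chance difference between arms in starting activity shifts the unadjusted rates, and the information that could correct for it goes unused. What is at stake is power and interval width in four dose comparisons per endpoint and time point.

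**Working it through.** **1. The plan's own figure.** SAP 6.1 gives 47, 48 and 47 per group for ACR20, with placebo rates 0.25, 0.35 and 0.45 and this premise: "Assuming the ACR20 of at least one of the JTE-051 doses to be at least 0.30 above placebo". Exact power of the two-sided Fisher test is the sum over all (x0, x1) of Bin(x0; n, p0) × Bin(x1; n, p0 + 0.30) × 1[Fisher p ≤ 0.05].

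- n = 47 / 48 / 47: 79.9% / 79.9% / 79.9%
- n = 50: 83.5% / 82.8% / 83.5%

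The figure reproduces, but it concerns ACR20 only. The documents state no rate, power or baseline-to-Week-12 correlation for the cut-off endpoints, so everything below rests on assumed values.

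**2. Simulation set-up.** There are 50 analysed per arm ("Approximately 250 eligible subjects (50 in each treatment group) are randomized into the DB treatment period of this study"; no dropout rate is given), two-sided 5%, and 8,000 trials per cell (Monte Carlo error about 0.5 points). The standardised baseline is Z and the latent final score is Y = ρZ + √(1 − ρ²)ε. A subject responds if Y < Φ⁻¹(p) for the arm's rate p. Three tests are compared:

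- Fisher's exact test;
- the unadjusted score test, z = (p̂1 − p̂0)/√(2p̄(1 − p̄)/50);
- the adjusted score test: fit logit P(response) = α + βZ without treatment, then U = Σ over the active arm of (y − μ̂), with its information adjusted for α and β; reject if |U/√V| > 1.96.

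Adjusted minus unadjusted score isolates the baseline. Unadjusted score minus Fisher isolates Fisher's conservatism.

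**3. Gain from the baseline alone (points of power).**

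| Placebo v active | ρ 0.2 | 0.3 | 0.4 | 0.5 | 0.6 |
|---|---|---|---|---|---|
| 0.01 v 0.08 | 1.4 | 1.0 | 1.2 | 2.6 | 4.6 |
| 0.02 v 0.12 | 2.5 | 3.4 | 4.1 | 5.6 | 7.9 |
| 0.05 v 0.20 | −0.3 | 0.8 | 2.1 | 4.3 | 6.9 |
| 0.10 v 0.20 | −0.7 | 0.4 | 0.9 | 2.2 | 4.7 |
| 0.10 v 0.30 | 0.4 | 1.1 | 3.3 | 5.3 | 8.2 |
| 0.20 v 0.35 | 0.6 | 1.8 | 3.2 | 4.9 | 9.0 |
| 0.20 v 0.45 | 1.8 | 2.6 | 4.3 | 6.4 | 9.8 |
| 0.25 v 0.55 | 0.5 | 1.3 | 2.6 | 4.2 | 6.2 |

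The small negative values are indistinguishable from zero. The gain is 2 points or more in every row only from ρ of about 0.5.

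**4. Splitting the total.** At 0.20 v 0.45 and ρ = 0.3, Fisher has 70.9%, the unadjusted score test 77.5% and the adjusted test 80.1%. Leaving Fisher gives 77.5 − 70.9 = 6.6 points, and the baseline gives 80.1 − 77.5 = 2.6. Fisher's conservatism costs about 4.5 points at 0.25 v 0.55, 9 to 10 at 0.10 v 0.30 and 15 at 0.05 v 0.20. None of that is due to the missing baseline.

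**5. Which form of the adjusted test.** At 0.02 v 0.12, the baseline-adjusted Wald test has 13 to 19% power against about 31% for Fisher. At a null rate of 0.05, the likelihood-ratio test rejects 8 to 9% of the time. The adjusted score test rejected 1.9 to 5.5% over null rates from 0.02 to 0.35.

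**6. Rule: adjusted score test with at least 10 events in the pair of arms, otherwise Fisher.** The exact binomial probability of fewer than 10 events is 84% at 0.02 v 0.12 (expected 50 × 0.14 = 7), 89% at 0.03 v 0.10 (expected 6.5) and 45% at 0.05 v 0.15 (expected 10). Simulating the whole rule (ρ 0.3 to 0.6, 4,000 trials per cell, Monte Carlo error for type I error about 0.35 points) gave type I error of 0.8–1.0 / 3.0–3.9 / 4.5–5.6 / 5.3–5.4% at null rates 5 / 10 / 20 / 30%. Power moved from Fisher to the rule as follows:

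| Rates | Fisher | Rule |
|---|---|---|
| 0.02 v 0.12 | 31% | 34–35% |
| 0.05 v 0.20 | 51% | 64–68% |
| 0.10 v 0.30 | 65% | 76–83% |
| 0.20 v 0.45 | 71% | 79–87% |
| 0.25 v 0.55 | 84% | 90–94% |

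Much of this improvement is the conservatism component from step 4.

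**The case against.** The strongest reply is that nothing here is broken. Fisher's test and the exact trend test are pre-specified and valid under randomisation, the endpoints are secondary in a Phase 2a trial with no power claim, and the same indices are analysed as continuous change with baseline adjustment. That stands, and it limits the point to precision. It does not remove it: the mixed model estimates a mean change, not the proportion reaching a target.

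A second reply is that SAP 6.4.8 (and Protocol 3.8.3.4) lets baseline enter parametric models where suitable. That could cover the GEE in principle, but the printed code leaves it out, and the clause cannot reach two tests that take no covariate. Nor does the comparison with the primary endpoint in SAP 6.4.2 clearly bring over its logistic models, since the text then names only the two tests. Even if it did, baseline PGA is one component of SDAI and CDAI and no part of DAS28-CRP.

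Third, the GEE adjusts for screening hs-CRP category, and CRP is a component of SDAI and DAS28-CRP. The simulated comparator has no strata, so the table measures the gain over an unadjusted test; the gain over the planned GEE was not measured. This stands.

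Fourth, for rare remission the proposed model would often hand back to the exact test. This also stands (step 6). Boolean remission has no baseline index of its own, and using SDAI for it was not simulated.

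**Conclusion.** The gap is real and inexpensive to close. Six fixed-threshold endpoints are tested without a prognostic baseline that the SAP already derives and already uses for the continuous forms. The size is conditional: at 50 per arm, about 0 to 3 points of power if the baseline-to-final correlation is 0.2 to 0.3, and about 5 to 10 points if it is 0.6. This assumes 50 analysed per arm, a latent-normal index, the rates in the table and pairwise comparisons. The trend test and the GEE were not simulated.

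A reader might infer more, and the documents do not support it:

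- **That the plan gives up a fixed amount of power, such as 2 to 10 points.** No correlation or rate is stated, and at low correlation the gain is close to nil.
- **That the whole distance between Fisher and an adjusted model is due to the baseline.** A large part is Fisher's conservatism.
- **That remission endpoints gain as much in practice as low disease activity.** With few events the exact test would usually decide.
- **That the planned tests are biased or invalid.** They are not.

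**What to change.** In SAP 6.4.2, add for the SDAI, CDAI and DAS28-CRP cut-off endpoints a logistic model by visit with treatment, the stratification factors and the baseline of the same index. State that the p-value comes from the score test, not from the default Wald or likelihood-ratio output. Report the adjusted odds ratio and a standardised risk difference, each with a 95% CI, and fit dose as a linear term for trend. Add the same baseline to the GEE code in SAP 6.4.3.

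Keep Fisher and exact Cochran-Armitage as planned. Specify in advance that the exact test carries the inference when a pair of arms has fewer than about 10 events. For Boolean remission, baseline SDAI may be offered as an optional proxy: it sums the same four components plus the physician's global score.

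The cost is SAP wording and modest programming on data already collected. Expect little or no gain for rare remission endpoints.

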6.4.3 Supportive Analyses of Efficacy Parameters

For dichotomous efficacy parameter analysis with multiple time points, a supportive analysis will be performed using a generalized estimating equation (GEE) method on the logit scale. The model includes effects for treatment, time, treatment by time interaction, stratification factors and subject as the repeated factor. The odds ratio (OR) of each JTE-051 dose group relative to placebo at the same time point will be estimated.

Model: (generalized estimating equation (GEE) method on the logit scale)

```
proc genmod data=xxxx;
  class usubjid trtn(ref=1) region(ref=0) hscrpn(ref=0);
  model SAEP=trtn time trtn*time regionn hscrpn;
  repeated subject=usubjid/type=un corrw;
run;
```

[figure not shown]
Note: SAPE denotes any dichotomous efficacy parameter, regionn and hscrpn are stratification factors, we can add other stratification when needed.

The supportive efficacy parameters utilizing the non-hs-CRP will be analyzed in a similar manner as their secondary efficacy counterparts using hs-CRP.

All analyses will be performed two-sided at the 5% significance level. No formal multiple comparison adjustment will be made; therefore, results should be interpreted with the multiplicity in mind. The estimated treatment effect (relative to placebo), e.g., odds ratio, from the model, along with a two-sided 95% confidence interval (CI) and p-value, will be tabulated where appropriate. The Newcombe's CI of the rate difference between JTE-051 dose and placebo will be computed when performing the Fisher's exact test. Graphical presentations of the treatment profile will be depicted for the primary and key secondary analyses. Sensitivity analysis and model fit assessment may be conducted, and data transformation may be employed if appropriate.

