6.4.1 Analyses of Primary Efficacy Endpoint

For the primary efficacy parameter (ACR20 response rate at EOT), the Fisher's exact test will be used to compare each JTE-051 dose group with placebo. Furthermore, the exact Cochran-Armitage trend test will also be performed, using the ordinal score for treatment, e.g., score 1 for placebo, score 2, 3, 4 and 5 will be used to represent JTE-051 50 mg, 100 mg, 150 mg and 200 mg, respectively.

Model (Fisher's exact test, will be performed by k=2, 3, 4, 5 separately)

```
proc freq data=xxx;
  table ARC20*trtn/chisq exact; ***trtn is the ordinal score for treatment***;
  where trtn in (1, k);
run;
```

Model (exact Cochran-Armitage trend test)

```
proc freq data=xxx;
  table ARC20*trtn/trend measures ci
    plots=freqplot(twoway=stacked);
  test smdr;
  exact trend;
run;
```

In addition, logistic regression model-based analyses will be performed for the pairwise comparisons between JTE-051 and placebo groups (Model 1) and for the evaluation of dose response relationship (Model 2). The logistic regression models will include the baseline PGA score, hs-CRP and region as a covariate.

Model 1 (pairwise treatment vs placebo comparison)

```
proc logistic data=xxx descending;
  class regionn hscrpn;
  model ACR20 = PGA Dose_50 Dose_100 Dose_150 Dose_200 regionn hscrpn;
run;
```

Model 2 (dose-response analysis)

```
proc logistic data=xxx descending;
  class regionn hscrpn;
  model ACR20 = PGA Dose regionn hscrpn;
  oddsratio Dose;
run;
```

Note:

- In Model 1, Dose_x = 1 if dose=x; otherwise. Dose_x=0; i.e., Dose_x is a dummy variable.
- In Model 2, Dose = 0, 50, 100, 150, 200 for placebo and each JTE-051 dose level, respectively.
- ACR20 is a 0, 1 variable; i.e., ACR20=1 represents a responder; ACR20=0 represents a non-responder.
- Regionn=0 represents 'EMEA'; Regionn=1 represents 'Latin America' or 'North America'.
- Hscrpn=0 represents screening hs-CRP<=2 x upper limit of normal (ULN); Hscrpn=1 represents screening hs-CRP>2 x ULN.
- From the model fitting, one obtains adjusted odds ratios and corresponding p-values for the respective pairwise treatment comparison versus placebo.

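### SAP 6.4.3 promises a logit-scale GEE with odds ratios, but the printed GENMOD code requests no logit link and, as written, gives risk differences

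*SAP*

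**What the plan says.** SAP 6.4.3 commits to a scale in its text: "a supportive analysis will be performed using a generalized estimating equation (GEE) method on the logit scale". The heading over the code repeats it: "Model: (generalized estimating equation (GEE) method on the logit scale". The target is also explicit: "The odds ratio (OR) of each JTE-051 dose group relative to placebo at the same time point will be estimated". The section asks for the model-based effect, with the odds ratio as its example, to be tabulated with a two-sided 95% CI and p-value where appropriate.

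The printed PROC GENMOD block has these parts:

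- a PROC statement with no options;
- a CLASS statement, "class usubjid trtn(ref=1) region(ref=0) hscrpn(ref=0" (closing bracket cut), which does not list time;
- a MODEL statement, "model SAEP=trtn time trtn*time regionn hscrpn", which ends there;
- a REPEATED statement that sets only the subject and the working correlation.

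No ESTIMATE or LSMEANS statement follows. The note under the code reads "SAPE denotes any dichotomous efficacy parameter", so the response is binary. The response is spelled SAEP in the code and SAPE in the note; region appears in CLASS and regionn in MODEL.

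For comparison, the logistic models for the primary endpoint in SAP 6.4.1 open with "proc logistic data=xxx descending", and that section codes a responder as 1.

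**The concern.** Text and code describe different models. Nothing in the block asks for a logit. GENMOD's default for a single response variable is the normal distribution with identity link. That default is a property of the software named in SAP section 8 and is not stated in the documents, but the mismatch can be seen without it.

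Run as printed, apart from the variable-name slips, the program fits a linear probability model and need not give any warning that the scale is wrong. At stake is whether the supportive tables contain what the SAP promises. A programmer might report a risk difference in an odds ratio column, or exponentiate it. At the rates the SAP cites from the mavrilimumab study (0.69 and 0.40), the difference is 0.29 and the odds ratio is (0.69/0.31)/(0.40/0.60) = 3.34. Exponentiating the difference gives exp(0.29) = 1.34, which is neither quantity.

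**Working it through.** The SAP gives no figure for this analysis, so there is none to reproduce. The check has four steps.

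**1. Text against code.** The text and code heading require a logit link and odds ratios. The MODEL statement sets neither a distribution nor a link, REPEATED cannot set them, and no statement requests odds ratios. This is the contradiction.

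**2. Effect of the missing link.** The response curves are assumed; they are not in the documents. Placebo is 16/26/33/36/34% at Weeks 2/4/8/12/16. The top dose is 27/43/58/65% at Weeks 2 to 12, with Week 16 at 64, 57, 46 or 34%. The true Week 12 odds ratio is (0.65/0.35)/(0.36/0.64) = 3.30, and the true risk difference is 0.65 − 0.36 = 0.29. I solved the population GEE equations for two arms with linear week and arm-by-week terms, an independence working correlation and no covariates.

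On Weeks 2 to 12 the identity fit has a treatment coefficient of 0.0893 (the difference extrapolated to week 0) and a slope difference of 0.0178 per week. At Week 12 the difference is 0.0893 + 12 × 0.0178 = 0.303. The fitted Week 12 risks are 0.6834 and 0.3805, so a back-calculated odds ratio is (0.6834/0.3166)/(0.3805/0.6195) = 3.51.

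**3. Effect of linear time once the logit is restored.** On Weeks 2 to 12 the fitted odds ratios are 1.91/2.15/2.72/3.45, against true values of 1.94/2.15/2.80/3.30. With Week 16 included, the Week 12 results are as follows (true odds ratio 3.30, true difference 0.29):

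| Assumed top-dose rate at Week 16 | Identity: difference | Identity: back-calculated OR | Logit, linear time: OR |
|---|---|---|---|
| 64% | 0.273 | 3.08 | 3.16 |
| 57% | 0.244 | 2.73 | 2.78 |
| 46% | 0.199 | 2.28 | 2.30 |
| 34% | 0.150 | 1.87 | 1.89 |

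The code uses an unstructured working correlation. As a sensitivity check, AR(1) with 0.6 gives logit Week 12 odds ratios of 3.12/2.62/2.03/1.55 with Week 16 and 3.45 without it. In the last case the identity difference falls from 0.150 to 0.095.

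The last two columns nearly agree. On these curves the distortion comes from linear time combined with Week 16, and hardly at all from the missing link.

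**4. Cost of categorical time.** Treatment and time terms number 4 + 4 + 16 = 24 with five visits, or 4 + 3 + 12 = 19 with four, against 4 + 1 + 4 = 9 with linear time. A visit-level odds ratio has no finite estimate if either arm has no responders. With 50 per arm, one arm is empty with probability q = (1 − p)^50, and at least one of two independent arms with probability 1 − (1 − q)²:

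| Assumed rate p in both arms | q | Either arm empty |
|---|---|---|
| 1% | 0.605 | 84% |
| 2% | 0.364 | 60% |
| 5% | 0.077 | 15% |

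An empty placebo cell removes all four odds ratios at that visit.

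**The case against.** The strongest reply is that the block is a template, with a placeholder data set and response name and an invitation to add stratification terms. The prose and heading give the scale twice, so a competent programmer would supply the link. That stands as a reason to call the point minor. It does not remove the error, because the printed code can fit a different model without announcing it.

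Three stronger readings are tempting, and none is supported.

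- A reader might infer that no odds ratio can be obtained from the printed model. One can be formed from its fitted risks, as step 2 shows. The accurate statement is that its coefficients and contrasts are not odds ratios, and that the SAP plans no conversion.
- A reader might infer that the missing link badly biases the odds ratio. On the assumed curves it barely moves the Week 12 point estimate.
- A reader might infer that leaving time out of CLASS also contradicts the text. The text says only that time is in the model, and a model with linear time on the logit scale also gives an odds ratio at each time point. Categorical time is a recommendation.

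On visits, SAP 5.2.2 already lists Weeks 2 to 16 and end of treatment. SAP 6.4 defines end of treatment as the last on-treatment value, so it is not a separate visit. The open question is whether Week 16, about four weeks after the last dose, belongs in this model. The mock tables, which are a separate document, may answer it.

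**Conclusion.** Wrong as written, minor. The GENMOD block in SAP 6.4.3 does not request the logit-scale model that its own text and heading specify, and it does not output the promised odds ratios and confidence intervals. This conclusion rests on the printed text and on GENMOD's default, not on the assumed curves.

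Linear time and the role of Week 16 are matters to clarify. Under the assumed curves, linear time does little harm on Weeks 2 to 12 (3.45 against 3.30). It can distort the Week 12 odds ratio materially only if Week 16 enters and the effect is lost off drug. No document supports any particular Week 16 rate.

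The spelling slips need tidying. Because SAP 6.4.1 codes regionn as 0/1, its absence from CLASS does not change the fit.

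A reader should not carry this over to the main results. The Fisher, trend and logistic analyses of the primary endpoint (SAP 6.4.1) and the by-visit tests (SAP 6.4.2) are unaffected.

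**What to change.** **To match the text:**

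- Add `/ dist=bin link=logit` to the MODEL statement.
- Add `descending` to the PROC statement, as in the logistic models of SAP 6.4.1, so that the responder is the event. Without it a binomial fit would by default model non-response, and an odds ratio of 3.30 would appear as 1/3.30 = 0.30.
- Add ESTIMATE statements with the EXP option, or an equivalent, for each dose against placebo at each visit, with 95% CI.
- Use one spelling each for regionn and the response variable.

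**Recommended separately:**

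- Put time in CLASS and add `within=time` to REPEATED, so that each visit's odds ratio is not tied to a linear trend.
- State in one sentence which visits enter, whether Week 16 is among them, and that end of treatment is not a separate time level.
- State in one sentence that for sparse endpoints such as remission the planned by-visit Fisher test and its interval will be relied on. The interval is already in the plan: "The Newcombe's CI of the rate difference between JTE-051 dose and placebo will be computed when performing the Fisher's exact test".

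**Cost:** a few words of code and two sentences, with no effect on data or timelines. The statistical price of categorical time is the extra parameters and the non-estimable odds ratios in step 4, which is why the sentence on sparse endpoints is needed.
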